Diabetes Risk Assessment and Medical Referral or Signposting (DRAMeRS) Study Protocol

Protocol version number: Version 4 23/05/2022 IRAS number: 306747 Sponsor number: Dental/VT/01

Study Contacts:

Chief	[name], NHS Education for Scotland [contact]		
Investigator			
Sponsor	NHS Education for Scotland		
Study Team	[name], NHS Education for Scotland	[contact]	
	[name], NHS Education for	[contact]	
	Scotland		
[name], University of Aberdeen		[contact]	
[name], NHS Education for Scotland		[contact]	
	[name], University of	[contact]	
	Aberdeen		
	[name], NHS Education for Scotland	[contact]	

Study Summary

Study Title	Diabetes Risk Assessment and Medical Referral or Signposting (DRAMeRS)		
Study Design	A two-arm clustered randomised controlled trial		
Study	Eligible dental patients and dentists working in vocational training practices		
Participants			
Planned Sample	140 dental vocational training practices		
Size	Each participating dentist should recruit 20 patients		
Follow-up	One month		
Duration			
Planned Study	February – December 2022		
Period			
Research Aim	The aim of the study is to compare the effectiveness of two referral strategies		
	(direct referral and signposting) at facilitating contact between dental patients		
	assessed as being at moderate or high risk of developing type 2 diabetes and a		
	healthcare professional.		

1. Background and Rationale

Evidence suggests that dental settings present a potential opportunity to conduct general health checks with patients. Yonel et al. found out that of patients who were regular dental attenders, almost half of them claimed that they had never gone for routine health check at their GP. Furthermore, patients, members of the public, GPs and GDPs were all in favour of screening for non-communicable diseases such as diabetes in dental practices and community pharmacies.¹ In a survey of patients' attitudes towards health screenings in dental settings, 87% of dental patients in South-West England thought that it was imperative that dentists screened patients for medical conditions and nearly 90% also indicated willingness to let a dental team conduct a health screening.²

The introduction of general health checks in dental practices was proposed in the 2018 Scottish Oral Health Improvement Plan (OHIP), a strategic framework for improving the oral health of the Scottish population³, which had a focus on prevention and included a section on general health checks for adults. This suggested that dentistry could utilise its cohort of regular attenders by conducting general health checks for the early detection of chronic diseases. It outlined actions for the Scottish Government, one of which was to "explore the potential for introducing general health checks for adult patients whilst attending for routine dental checks" ⁵. This suggests that this research exploring the use of general health checks in dentistry could provide valuable information to inform the implementation of this aspect of the OHIP framework.

Evidence suggests that participation in general health checks can vary considerably. Harte et al. (2018) explored reasons for non-attendance at NHS Heath Checks in England. These checks were available at GP practices, pharmacies and other community settings. The authors found that misunderstanding the purpose of the checks, aversion to preventive medicine, difficulty accessing GP practices, and concerns about pharmacies as an appropriate setting for these checks, all contributed to non-attendance.⁴ This suggests that there are numerous potential barriers to introducing general health checks in dentistry; this study will seek to explore this further by investigating the views of patients and dental professionals.

From a range of possible general health checks that could be implemented in dental practices for this study (e.g. blood pressure, heart rate), type 2 diabetes was chosen due to its established links with oral health. Indeed, when considering the links between oral health and general health, the common risk factor approach outlines how diabetes and oral health, specifically periodontal disease and dental caries, share several risk factors, including diet, smoking and stress. ⁵ There is a clear relationship between type 2 diabetes and periodontitis, with significantly elevated HbA1c levels in periodontal patients⁶. This relationship is considered to be bidirectional, with diabetes increasing the risk for periodontitis and periodontal inflammation negatively impacting glycaemic control, as well as a clear association between the degree of hyperglycaemia and severity of periodontitis.

A systematic review and meta-analysis of the current evidence identified that dental patients could be identified as having undiagnosed type 2 diabetes and non-diabetic hyperglycaemia when a point-of-care, opportunistic screening was used in a dental setting⁷. Furthermore, in research carried out by Lalla et al., more than one third of dental attenders with unrecognised hyperglycaemia were successfully identified in dental settings by using a diabetes risk questionnaire, periodontal screening and a point-of-care HbA1c test. This has suggested that dentists have a significant role in identification of unrecognised diabetes and pre-diabetes.⁸

Diabetes UK is the leading diabetes charity in the UK⁹. Available via their website, they have developed a risk assessment tool that the public can use to determine their risk of developing type 2 diabetes. This tool is based on the Leicester Diabetes Risk Assessment, a validated questionnaire which was designed to be completed by a lay person with the aim of screening and identifying individuals at high risk of impaired glucose regulation and type 2 diabetes mellitus.¹⁰ The assessment tool asks for the following information: gender, age, ethnic background, if you have a close relative with diabetes, waist

measurement, height, weight, and if you have high blood pressure. Your risk level is then calculated. You can either be high, moderate, increased or low risk. Diabetes UK recommends that you should visit your GP for a blood test to check for diabetes if you are moderate or high risk¹¹. This tool has been chosen to be the health check used in this study.

There is limited evidence available regarding comparison of signposting or directly referring patients to a healthcare professional. Burns et al. (2021) considered this in relation to interventions that linked families from healthcare services to community-based support. Their study found that the more active the act of linking was, the more successful it was at linking families to support, i.e. referral was more successful than signposting.¹² More evidence is required however, regarding the use of signposting and referral in a dental setting, to another healthcare professional.

Role of Vocational Dental Practitioners

In Scotland, dentists must undertake a 12 month "Vocational Training" (VT) year following completion of their undergraduate training. This VT year involves supervised clinical experience in an approved training practice. There are 140 training practices and these are spread throughout training schemes in 5 regions: North, North-East, East, South-East, and West. Satisfactory completion of the VT year permits dentists to be eligible for an NHS list number which allows a practitioner to become an associate or a principal in the NHS General Dental Service (GDS) or a salaried dentist in the Public Dental Service (PDS). The aim of the VT year is to provide dental graduates with the skills necessary to undertake unsupervised clinical work, as well as enhance their skills and competence with the clinical and non-clinical aspects of dentistry.¹³

During the COVID-19 pandemic the provision of dental services in Scotland was severely disrupted. In March 2020, most routine care ceased, with NHS dental practices closed to patients but providing telephone triage¹⁴. Dental practices were allowed to re-open in June 2020. They were initially restricted to urgent, non-aerosol generating procedures, but by August were allowed to conduct non-urgent aerosol generating procedures, with restrictions still in place regarding personal protective equipment and the mitigation of aerosol generation¹⁵. These closures and restrictions have had a significant impact on the numbers of patients that can be treated, leading to backlogs and waiting lists. This also impacted upon VT, resulting in VDPs who had not gained sufficient clinical experience during their 12-month post¹⁶. As such, a decision was made to extend the 2020-2021 VT year until August 2022, giving the current cohort of VDPs an additional 12 months in which to gain sufficient clinical experience¹⁷.

This additional year was also considered to be an opportunity to provide VDPs with first-hand experience of undertaking a research project. As such, a project team was established with staff from NHS Education for Scotland's Clinical Effectiveness and Vocational Training workstreams, alongside researchers from the University of Aberdeen and a group of VDPs. Twenty-one VDPs volunteered to be involved in the study design process; these VDPs participated in design workshops and have contributed to this protocol and produced supporting resources. They will also be involved in data collection, data analysis and dissemination.

2. Aims and Objectives

2.1. Aim

To compare the effectiveness of two referral strategies (direct referral and signposting) used by primary care dentists for facilitating contact between dental patients assessed as being at moderate or high risk of type 2 diabetes and a healthcare professional.

2.2. Objectives

Primary objective:

To compare the effectiveness of the following referral strategies for facilitating contact between healthcare professionals and patients at risk of type 2 diabetes:

- Direct referral
- Signposting

Secondary objectives:

- to explore the beliefs and experiences of primary care dentists about general health checks and referral in primary care practice.
- to explore the beliefs and experiences of dental patients about general health checks and referral in primary care practice.

3. Method

3.1. Study Design

A two-arm clustered randomised controlled trial.

3.2. Study Setting

This will be a multi-centred study, with patient recruitment and data collection taking place in vocational dental training practices across Scotland. Once recruited, each participating dental practice will receive information and training regarding what is required from their practice before the study can begin, and what they will be expected to do regarding data collection and data storage.

3.3. Sample, Recruitment and Eligibility

All dentists (principal, associate, VDP) working in vocational training practices in Scotland will be contacted via existing vocational training networks inviting them to take part. Eligibility criteria is shown in Table 1.

Participant	Inclusion	Exclusion	
Group			
Practices	vocational training practiceBased in Scotland	Not a vocational training practiceOutside of Scotland	
Practitioners	 Dentist working in a vocational training practice in NHS General Dental Service VDP Principal dentist Associate dentist Private dentists 	 Practitioners in: Public Dental Service Hospital Dental Service 	
Patients	 Adults ≥ 40 years Attending a vocational training practice for a non-emergency appointment English speaking 	 Adults < 40 years Patients attending for emergency treatment Patients who are pregnant Patients who have been previously diagnosed with diabetes or non-diabetic hyperglycaemia Patients who do not speak English 	

Table 1: Eligibility criteria for all participant groups

Patients will be recruited via communication from their dental practices. Patients will be contacted about the study when they receive their standard appointment reminder message. This can be via email or the patient's preferred method of communication. This recruitment message will contain information about the project and the participant information sheet will also be provided. Patients will be advised that if they wish to take part in the project they should bring their height, weight and waist measurements with them to their next appointment. At the appointment they will be assessed for their eligibility, given the opportunity to ask questions about the study, and asked to consent to their participation.

3.4. Randomisation

All eligible NHS dental training practices in Scotland will be invited to take part (n=140). Eligible practices agreeing to take part will be randomised to either signpost or directly refer patients to their GP if their risk assessment score was "moderate" or "high". An automated system will randomise eligible practices on a 1:1 basis. A computer-generated stratification programme, incorporating a random element, will ensure intervention arms are balanced for practice size.

3.5. Intervention groups

There will be 2 intervention groups. Practices in Group 1 will signpost their patients to a healthcare professional. Practices in Group 2 will directly refer their patients to a healthcare professional (see Figure 1).

3.6. Outcomes

Primary: the proportion of patients who make contact with a healthcare professional. Contact may be in person or via the telephone. Healthcare professional may include the patient's GP or pharmacist.

Secondary: beliefs of patients and dentists regarding the acceptability of general health checks in a dental setting and their feelings about being told their risk level.

3.7. Sample size

Our sample size calculation is pragmatic and, therefore, based on the number of sites available to do this study (140 sites). The study will randomise practices on a 1:1 basis, so each arm will have 70 sites. Participating dentists in each site will be asked to recruit 20 patients each. The study will be randomised and analysed at the practice (cluster) level; therefore we implemented a formulae for individually randomised trials using Stata's 16 power command. Assuming 55% of participants will contact a healthcare professional about their risk score if it is elevated, which is supported by evidence coming from a similar and recent study¹⁸, and assuming a standard deviation of 25%, we have 80% power to detect a difference of 12% between arms, equivalent to 67% of participants contacting their healthcare professional in the intervention arm. We assumed no drop-out as the sample size is calculated according to the number of clusters (practices) and we do not expect practices to drop out.

3.8. Data Collection

Once a patient has been confirmed as being eligible to participate, and has consented, the dentist will then complete the risk assessment online tool with the patient. The patient will be informed before

attending the appointment what information they will need, and will be asked to take their own measurements (weight, height, waist circumference) before attending. They will be provided with information beforehand about how to take these measurements. Participating dentists will be required to keep a record of the number of patients they conduct the risk assessment with, and the outcome of that assessment, i.e. the patient's risk assessment score, and what action was taken. This information will be stored in the Case Report Form.

Both signposting and referral will involve standardised resources, developed by VDPs. Dentists who signpost patients will be provided with an information leaflet with key information for patients. Dentists who make a direct referral to their patients' GP practice or pharmacist will be provided with a standardised referral letter template. This letter can be customised with patient details and then hand delivered or emailed to the patient's GP practice or pharmacist.

An online self-report survey will be sent to all patients one month following their risk assessment. Paper copies will be available for participants who have not supplied an email address, or who do not have internet access. For patients who were at moderate or high risk, they will be asked if they have contacted a healthcare professional about the outcome of their risk assessment. Due to the impact of COVID-19 restrictions, attendance at a GP practice in person may not be possible; as such, we will consider any verbal contact with GP or other healthcare professional, either in person or via telephone, as "contact" for the purposes of this study. This survey will also measure the secondary outcomes for all patients, i.e. their beliefs and experiences about receiving a general health check. Patients will be asked about their thoughts on the acceptability of general health checks in a dental setting, how they felt about being told their risk score and how they felt about being referred/signposted if they were at moderate or high risk. Demographic information will also be collected. A flow diagram of the patient journey is presented in Figure 2.

Figure 2: Patient Journey

An online survey will be sent to participating dentists, asking about their beliefs and experiences about conducting the risk assessment in their practice, as well as their thoughts on general health checks in dentistry. They will also be asked how they felt about telling their patients their risk score.

In addition, a small sub-group of participants (dentists and patients; n=10 per participant group) will be invited to take part in interviews. This qualitative approach will allow for a deeper understanding of the beliefs and attitudes of participants. Interviews will be conducted online via Microsoft Teams or via telephone, depending on participant preference. All interviews will be audio-recorded using a separate audio-recording device; Microsoft Teams will not be used to record interviews. These interviews will be transcribed by the study administrators for the purposes of data analysis.

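### The protocol is inconsistent on whether contact started by the GP practice or pharmacist counts, and a literal survey item could under-count contact in the direct-referral arm only

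*Protocol*

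**What the plan says.** Two places are neutral on who starts the contact.

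- Section 2.1 (Aim) compares the two strategies "for facilitating contact between dental patients assessed as being at moderate or high risk of type 2 diabetes and a healthcare professional".
- Section 3.8 (Data Collection) says "we will consider any verbal contact with GP or other healthcare professional, either in person or via telephone" to be contact for the study. The sentence is introduced by reference to COVID-19 limits on attending in person.

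Three places describe an act by the patient.

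- Section 3.6 (Outcomes) defines the primary outcome as "the proportion of patients who make contact with a healthcare professional".
- Section 3.8 says of moderate- and high-risk patients that "they will be asked if they have contacted a healthcare professional about the outcome of their risk assessment".
- Section 3.9 (Data Analysis) estimates a difference in the average proportion of patients doing the contacting.

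The arms differ in who is told. Under direct referral, section 3.8 has a letter that is "hand delivered or emailed to the patient's GP practice or pharmacist". Under signposting, "Dentists who signpost patients will be provided with an information leaflet with key information for patients", and no message to the GP practice is described.

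**The concern.** A referral letter gives the recipient a reason to telephone or invite the patient. A leaflet does not. Contact started by the professional is therefore a plausible route in one arm and an unlikely one in the other. A patient who was telephoned, and who made no approach of their own, can truthfully answer no when asked whether they have contacted a professional. Under the aim that patient has had contact; under a literal reading of the item they have not.

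Misclassification of this kind would depend on arm and run in one direction, against direct referral. It would also act on the feature that separates the arms. The protocol describes no second source that could recover such contacts: the primary outcome rests on a single self-report at one month, the Case Report Form holds the risk score and the action taken by the dentist, and section 5.1 says the study team has no access to patient records.

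**Working it through.** **1. Do the passages agree?**

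| Place | Who acts | Does a call from the GP practice count? |
|---|---|---|
| 2.1 Aim | either side | yes |
| 3.6 Primary outcome | patient | unclear; not on a literal reading |
| 3.8 Survey item as described | patient | unclear; not on a literal reading |
| 3.8 Any verbal contact | not specified | yes on its wording, though written to settle mode |
| 3.9 Analysis | patient | unclear; not on a literal reading |

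No sentence says expressly that contact started by the professional counts, or that it does not.

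**2. The plan's own figure.** Inputs from section 3.7: 70 practices per arm, 55% against 67%, standard deviation of practice proportions 25%. Section 3.7 gives no alpha; two-sided 5% is assumed, in line with the 95% confidence intervals in section 3.9.

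- Standard error of the difference = 0.25 × √(2/70) = 0.0423.
- Noncentrality = 0.12 / 0.0423 = 2.84.
- Power = 80.5% by noncentral t with 138 degrees of freedom, or 81.1% by the normal approximation. The stated 80% reproduces.

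**3. Illustration of a one-sided loss.** Let f be the share of true direct-referral contacts that were started by the professional and are answered no. Assume that direct referral is the 67% arm, that nothing is lost under signposting, and that the standard deviation stays at 25%. Then

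observed difference = 0.67 × (1 − f) − 0.55.

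| f | Observed direct-referral rate | Observed difference | Power (t) |
|---|---|---|---|
| 0% | 67.0% | 12.0 points | 80.5% |
| 5% | 63.65% | 8.7 points | 53% |
| 10% | 60.3% | 5.3 points | 24% |
| 15% | 56.95% | 2.0 points | 7% |
| 17.9% | 55.0% | 0 | – |
| 20% | 53.6% | −1.4 points | – |

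The difference vanishes at f = 0.12 / 0.67 = 17.9%. The documents give no value of f. The table shows how sensitive the comparison is; it does not estimate the bias.

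**The case against.** The strongest reply is that the protocol already covers these contacts. The sentence directly after the survey description counts any verbal contact, by telephone or in person, and a call from the practice is verbal contact by telephone. This stands in part, because the wording does not exclude contact started by the professional. But the sentence was written to settle mode, and it is a rule for the study team. It cannot turn a patient's no into a yes unless the survey also records that the professional called. If it is read as neutral on who starts the contact, it sits awkwardly with section 3.6 and with the item described just before it.

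Three further replies stand.

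- Section 3.8 summarises the survey item and does not reproduce it; the real item may carry the broader definition.
- The text does not say that a GP practice or pharmacist will approach the patient after the letter. Figures 1 and 2, which might show this, are not available in the text reviewed.
- To count towards f, a patient must have been contacted within the month, have made no contact of their own, and have read the question literally. Nothing in the documents supports a particular share.

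It is also possible that the patient's own act was the intended endpoint in both arms. Nothing would then be mismeasured, but the outcome would be narrower than the aim in section 2.1, and the protocol would still need to say so.

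A reader might infer that the survey does miss these contacts and that the primary comparison is biased. The documents do not support that: it needs an item not shown, an action by the recipient not described, and a share not given.

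**Conclusion.** The point holds as an inconsistency in the definition of the primary outcome, with a conditional risk attached. Sections 2.1 and 3.8 (any verbal contact) do not depend on who starts the contact; sections 3.6, 3.8 (survey item) and 3.9 are worded as the patient's act. If the item follows the literal wording and recipients of referral letters do approach patients, under-ascertainment would fall on direct referral and the reported difference would be too low for that arm.

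The size is unknown. On the assumptions above, a loss of 5% to 10% would take the planned power from about 80% to between 53% and 24%. A loss beyond about 18% would reverse the sign, but such a reversal is a scenario and not something that the text predicts. The inconsistency itself is clear from the text; the occurrence and size of any bias are not. It deserves correction because it concerns the single primary comparison, and analysis cannot recover an answer to a question that was not asked.

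**What to change.** - In section 3.6, state that contact counts whoever starts it, and align the wording of sections 3.8 and 3.9.
- Word the one-month item to match, for example: 'Have you spoken, in person or by telephone, with a healthcare professional about your risk result, whether you contacted them or they contacted you?'
- Add a tick-box for who initiated the contact, reported descriptively by arm.
- If the item in use asks only about the patient's own act, flag the responses already collected with it so that they can be told apart in the analysis.

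The cost is a small amendment: a sentence in section 3.6, one reworded item and one tick-box. The downside is possible mixed wording among early responses. The sample size does not change.
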